# I: TITLE

Acromegaly: balance, falls and fracture risk.

- List of abbreviations:
- **GH: Growth Hormone**
- IGF-1: Insulin-like Growth Factor 1
- SSA: Somatostatin Analog
- DA: Dopamine Agonist
- HR-pQCT: High Resolution peripheral Quantitative Computed Tomography
- HGS: Hand Grip Strength
- TUG: Timed Up-and-Go
- DXA: Dual X-ray Absorptiometry
- BMSi: Bone Material Strength Index
- vBMD: Volumetric Bone Mineral Density
- BMI: Body Mass Index
- VFA: Vertebral Fracture Assessment
- mSv: Milli-Sievert
- CoP: Center of Pressure
- WOMAC: Western Ontario and McMaster universities osteoarthritis Index
- FES-I: Falls Efficacy Scale International
- P1NP: procollagen-1 N-terminal propeptide a marker of bone formation) and
- CTX: cross-linked C telopeptide of type I collagen
- PTH: Parathyroid Hormone

#### **EPJ: Eletronic Patient Journal**

# **II: BACKGROUND, AIMS AND HYPOTHESES**

#### A. BACKGROUND

Acromegaly is a rare systemic disease characterized by hypersecretion of growth hormone (GH) from a pituitary adenoma, and consequently pathologically high levels of insulin-like growth factor I (IGF-I). Symptoms develop insidiously and include acral growth, coarse facial features and organ enlargement. The incidence of acromegaly is most often reported to be approximately 3-5 cases per 10^6 per year whereas the reported prevalence varies considerably between studies from 20 - 85 cases per 10^6 .

Acromegaly is associated with several comorbidities including diabetes mellitus, hypertension, heart failure, thromboembolic events, ischemic heart disease, increased cancer risk, arthropathy and osteopathy, and untreated it is associated with a significant reduction in quality of life and life expectancy.

The preferred treatment, when feasible, is transsphenoidal surgical removal of the pituitary adenoma, which is performed in 60-80% of patients in Denmark. Medical treatment includes somatostatin analogs (SSAs), the GH receptor antagonist Pegvisomant and dopamine agonists (DAs), while radiotherapy is rarely used. With optimal treatment and normalization of GH and IGF-I, acromegalic patients have a mortality rate close to that of the general population. If left untreated, however, acromegaly is associated with an increased mortality, mainly due to cardiovascular complications.

### **B. ACROMEGALY AND MUSCULOSKELETAL DISORDERS**

Of the acromegaly-related comorbidities, arthropathy is associated with a markedly reduced quality of life due to pain, reduced mobility, impaired activities of daily living as well as reduced work productivity and increased risk of early retirement. Arthropathy is one of the most frequent complications of acromegaly, affecting more than 70% of all patients. Acromegalic arthropathy is characterized initially by cartilage hypertrophy, joint space widening and osteophytosis, whereas in later stages it assumes features similar to primary osteoarthritis, such as joint space narrowing, subchondral cysts and bone edema. In early stages of acromegalic arthropathy, progression of the condition may be halted or even reversed by achieving biochemical control/remission, but in later stages the arthropathy becomes irreversible and persistent even despite successful treatment of the underlying condition. However, acromegalic arthropathy has even been found to slowly progress despite achievement of disease control. No effective treatment, except for surgical arthropatsy and analgesics, exists for this debilitating condition. Novel imaging techniques such as HR-pQCT have not yet been applied in the field of acromegalic arthropathy, and may further our understanding of the condition, potentially leading to new treatment options. HR-pQCT imaging of joints is common in research regarding inflammatory joint diseases, but thus far, no studies exist regarding HR-pQCT joint imaging in acromegalic patients.

Studies concerning balance and falls among acromegalic patients remain scarce. Thus far, it has been suggested that acromegalic patients have impaired balance and postural control, due to factors such as alterations in body composition, enthesopathy, myopathy, arthropathy or visual field disturbances. Indeed, altered body composition has been demonstrated in acromegalic patients using whole-body DXA scans and reduced peripheral muscle strength has been found using hand grip strength (HGS) as a measure. Moreover, an increased fear of falling has been observed in patients with acromegaly, although the frequency of falling seems to be similar to healthy controls. However, fall risk, as evaluated via the timed up-and-go (TUG) test, has been shown to be increased in acromegalic patients. An improvement in several dynamic balance parameters, as evaluated by stabilometry, has been demonstrated among acromegalic patients after a relatively short training program, indicating a potential benefit of focused physical therapy for this patient group. Given that acromegalic patients have impaired bone quality, preventing falls may be of considerable clinical relevance. However, this subject calls for further investigations. To our knowledge, no studies have directly compared body composition and dynamic muscle parameters such as hand grip strength, leg extension strength, timed up-and-go and stabilometry in acromegalic subjects.

Acromegaly-related osteopathy has been a subject of interest in recent years, as it has been established that patients with acromegaly have increased bone turnover, reduced bone quality and an increased risk of fractures despite normal bone mineral density as assessed by DXA-scans. Secondary hypogonadism due to tumor mass effect or pituitary surgery plays a significant role in the diminished bone quality of acromegalic patients, even after disease control is achieved.

Acromegalic subjects have been found to have reduced quality of the trabecular bone compartment, increasing the risk of vertebral fractures, which have indeed been found to be prevalent among acromegalic patients. Using High-Resolution peripheral Quantitative Computed Tomography (HR-pQCT), significantly reduced measurements of both trabecular and cortical volumetric bone mineral density (vBMD) have been reported in acromegalic patients, even during biochemical disease control. Disease duration and presence of hypogonadism appear to be the most influential risk factors for this impaired bone quality, although even eugonadal acromegalic patients have reduced trabecular bone quality. HR-pQCT-derived bone parameters can be used to calculate physical properties such as bone stiffness and failure load, which has previously been performed in acromegalic patients, revealing no difference between acromegalic patients and healthy controls in this regard. However, compromised bone quality has been confirmed *ex vivo* by means of iliac crest bone biopsies in a study of acromegalic patients, reporting both lower trabecular thickness and increased trabecular separation in acromegalic patients with vertebral fractures but normal BMD, as assessed by DXA scan.

Although normal or even increased cortical bone thickness has been reported using iliac crest bone biopsies, hip structure analysis and high-resolution cone beam tomography, other cortical bone parameters such as bone material strength index (BMSi) have been shown to be reduced, even in wellcontrolled acromegalic patients, suggesting compromised bone fracture resistance in acromegalic patients. Decreased BMSi, as measured by micro-indentation using an OsteoProbe, has been shown to be correlated with fragility fractures in postmenopausal women and in individuals with diabetes. Only one study has measured BMSi on acromegalic subjects and found significantly lower values compared to healthy controls, regardless of biochemical control, hypogonadism or presence of vertebral fractures. If and how BMSi values correlate to reduced bone quality, as assessed by HR-pQCT, remains to be examined in patients with acromegaly. Thus far, no studies exist regarding the integration of HR-pQCT-derived bone parameters, BMSi and the presence of vertebral fractures. By combining these diagnostic modalities, we aim to perform an integrated assessment of bone quality in acromegalic patients, examining both the cortical and trabecular bone compartments to further our understanding of acromegalic osteopathy. This may provide more insight into which diagnostic modality is optimal as a measure of fracture risk in acromegalic patients, since standard DXA scans have proved less useful in this regard.

#### C. OBJECTIVES

Aim:

A. To perform a comprehensive, integrated assessment of balance, bone and joint quality, body composition, muscle strength, fear and risk of falling and fracture risk of acromegalic patients.

#### Hypotheses:

A. Acromegalic patients have impaired bone quality (as assessed by HR-pQCT and BMSi), impaired balance, and increased risk of falling. Combining multiple diagnostic modalities will improve our understanding of the pathophysiological mechanisms behind acromegalic osteopathy.

# **III: METHODS**

# A. STUDY DESIGN

The study will be performed as a cross-sectional study examining patients with acromegaly and healthy controls. Participants will be informed about the study both orally and in writing and will be recruited from the pituitary endocrinology outpatient clinic at Aalborg University Hospital.

Healthy controls will be recruited via social media and websites such as www.forsøgsperson.dk. An existing database where participants have given written consent (within the last year) to be contacted regarding research projects may also be used. This database is created and administrated by the North Denmark Region, and approved by its legal staff. Potential participants are required to use a secure access (NemID), and if they do not actively renew their consent within a year, it is automatically withdrawn.

#### **B. STUDY POPULATION**

We plan to include thirty male or female patients with acromegaly and thirty age- (+/- 5 years), BMI- (+/- 5 points), and sex-matched non-acromegalic control subjects.

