# D. STUDY PROCEDURES

Patients with an established diagnosis of acromegaly will be recruited from December 2022 to March 2025. Patients will be informed of the study during scheduled visits to the pituitary endocrinology outpatient clinic at Aalborg University Hospital by one of two specialists in pituitary endocrinology. Patients will be given information regarding the study, and if interested, they will be provided with a form to fill out with their contact information, so they can be contacted by the investigators or other staff affiliated with the study. Should the patient agree to be contacted via telephone or e-mail, they will be given an instruction regarding their rights as a participant in a scientific study ("Dine rettigheder som forsøgsperson i et sundhedsvidenskabeligt forskningsprojekt") as well as written material specifically pertaining to the study ("Deltagerinformation"). Should the subject be deemed fit for the study, based on the in- and exclusion criteria, contact will be made via phone or e-mail and they will receive further information regarding the study, and offered a personal meeting with one of the investigators, where details of the study procedures will be outlined. The meeting will take place in a dedicated, undisturbed office at the disposition of the Department of Endocrinology, in order to ensure due privacy during the meeting. In advance, the subject will be informed of the opportunity to bring a relative or other representative to the meeting. At the meeting, the participant and any representative will be informed of the 24-hour deliberation period before providing informed consent. No study procedures will be performed until the informed consent form has been signed by both the participant and the investigator.

As mentioned above, healthy controls will be recruited via the aforementioned database, social media and websites such as www.forsoegsperson.dk. Potential participants who contact the principal investigator through these channels will be provided with written material pertaining to the study ("Deltagerinformation") and a description of their legal rights as a participant (*"Dine rettigheder som forsøgsperson i et sundhedsvidenskabeligt forskningsprojekt"*). Should the potential participant meet the inand exclusion criteria, they will be invited to a personal meeting, where details of the study are explained,

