#### BIOCHEMICAL BONE MARKERS AND BLOOD SAMPLES

To assess biochemical markers of bone metabolism, we will measure fasting serum levels of procollagen-1 N-terminal propeptide (P1NP, a marker of bone formation) and cross-linked C telopeptide of type I collagen (CTX, a marker of bone resorption) as well as sclerostin (an inhibitor of bone formation). To assess other hormones with influence on bone quality, we will measure levels of vitamin D and parathyroid hormone (PTH). In total, a volume of approximately 16mL of blood (4x 4mL vials) will be collected from each participant, both acromegalic and controls. For practical reasons, these blood samples are frozen after collection, stored in a research biobank, and analyzed in one session upon all participants' completion of the study procedures. Before analysis, Danish Tissue Utilization Register (Vævsanvendelsesregistret) will be consulted; should the participant be listed herein, the blood sample will not be analyzed. After analysis, any remaining material will be destroyed.

Two extra vials of blood (10mL total) will be extracted and stored in a biobank for future research, to enable analysis of any future bone markers or other biomarkers of interest for this project. An application will be submitted to the Danish Data Protection Agency in this regard. Blood samples will be frozen and stored in an encrypted fashion and in compliance with the Danish Data Protection Act for 15 years after completion of the study, or until their destruction is requested by the participant. Blood samples will be collected from both acromegalic subjects and healthy controls, in order to determine differences in biochemical markers between acromegalic subjects and control subjects. Participants will be asked to sign a separate consent form regarding storage of their biological material (blood sample) in a biobank for future research.

All blood samples are stored in a freezer at -80 degrees Celsius. The freezer is located on the premises of Aalborg University Hospital ([name]) and is only accessible by authorized personnel. Sample vials are marked only with a participant number, and the key to link each participant number to a specific participant will be stored on a secure server only accessible by personnel affiliated with the study.

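### Controls are not matched on when they are examined, and no adjustment for season is planned, so the vitamin D (and possibly PTH) comparison could mix season with disease

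*Combined protocol and SAP*

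**What the plan says.** Section III.B (Study population) sets out thirty patients and thirty age-matched (within 5 years), "BMI- (+/- 5 points), and sex-matched non-acromegalic control subjects". Those three factors are the whole matching rule.

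Section III.D (Study procedures) states: "Patients with an established diagnosis of acromegaly will be recruited from December 2022 to March 2025". It adds that "Patients will be informed of the study during scheduled visits to the pituitary endocrinology outpatient clinic". Controls come through social media, websites and a regional contact database (III.A, III.B, III.D). They are to be matched to the patients, but the plan gives neither a recruitment period for them nor an interval from the matched patient's visit.

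The subsection on biochemical bone markers in III.D plans fasting P1NP, CTX and sclerostin, and adds that "we will measure levels of vitamin D and parathyroid hormone (PTH"). It gives a comparison of patients with controls as a purpose of the blood sampling. It also says that "these blood samples are frozen after collection, stored in a research biobank, and analyzed in one session" once all participants have finished, with storage at -80 degrees Celsius.

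Section V.A (Statistical methods) lists t-tests, chi-squared tests and Mann-Whitney U tests and names no covariate. Section VII (Study limitations) mentions only the single centre.

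**The concern.** The two groups enter by different routes. Patients are approached as their clinic appointments fall due. Controls volunteer through advertisements or are contacted from a database, and are chosen to fit the patients. With no date in the matching rule, the two sets of visits can fall in different parts of the year.

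Vitamin D is expected to vary with season at Danish latitudes, and PTH may follow it; this is general background, and the documents give no figure. An unadjusted test cannot separate a seasonal difference from a disease difference. The protocol measures these two hormones because they influence bone quality, so a spurious difference could also colour the interpretation of the bone findings.

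**Working it through.** **The plan's own figure.** For trabecular density, difference 30, SD 40, two-sided 5% (sidedness assumed), 80% power: n = 2 x (1.960 + 0.842)^2 x 40^2 / 30^2 = 27.9, so 28 per group. Power at 28 is 80.1% by the normal approximation and 78.7% by the noncentral t. The stated figure is reproduced, and nothing below changes it.

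**Inputs from the documents.** There are 30 participants per group. December 2022 to March 2025 is 28 calendar months inclusive, stated for patients only. The test is an unadjusted two-sample test at 5%.

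**Assumed inputs (not in the documents).** 25(OH)D follows a yearly cosine with amplitude A = 10 to 15 nmol/L and SD 25 nmol/L. Patients are spread evenly over the year. This is approximate: a 28-month window contains December to March three times and every other month twice, so those four months make up 12/28 = 43% of it rather than 33%. There is no true group difference.

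**Shift if all controls fall in one block.** For a block of angular width w centred on the seasonal peak or trough, shift = A x sin(w/2)/(w/2).
- Half-year (w = pi): factor 2/pi = 0.64.
- Quarter (w = pi/2): factor 2 x sqrt(2)/pi = 0.90.

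If the block centre lies at angle phi from the peak, the shift is multiplied by cos(phi). It is zero for a block midway between peak and trough. Averaged over all timings, |cos(phi)| = 2/pi = 0.64.

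**False-positive rate.** With d = shift/25, the test statistic is noncentral t with 58 degrees of freedom and noncentrality d x sqrt(30/2).

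| Control visits | A | Worst-case shift, nmol/L (SD) | Worst-case rate | Mean absolute shift over timing | Rate averaged over timing |
|---|---|---|---|---|---|
| One half-year | 10 | 6.4 (0.25) | 16.3% | 4.1 | 11% |
| One half-year | 15 | 9.5 (0.38) | 30.7% | 6.1 | 18% |
| One quarter | 10 | 9.0 (0.36) | 27.9% | 5.7 | 16% |
| One quarter | 15 | 13.5 (0.54) | 53.9% | 8.6 | 30% |

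A simulation that also lets individual dates vary within each group gives slightly lower averaged rates: 10 to 16% for the half-year and 16 to 29% for the quarter. At A = 5 with a peak-centred block, the rates are 8 to 10%.

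**Partial clustering.** Let S be the summer-winter swing in within-season SDs and q the gap between groups in the share examined in summer. Then d = S x q / sqrt(1 + S^2 x p(1 - p)), with p = 0.5 + q/2. For q = 0.2, S = 0.5 gives d = 0.097 and a rate of 6.6%; S = 1.0 gives d = 0.180 and 10.5%. For q = 0.4 the rates are 11.5% and 28.3%. On the cosine model, A = 10 corresponds to S = 2 x 6.4/25 = 0.51.

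**Storage time.** A t-test is biased by the difference in group means. If patients are spread evenly over 28 months, their mean is at month 14. Even if every control is seen at the very end of that window, the means differ by 28 - 14 = 14 months. The documents give no degradation rate. Assuming drift of 0.1 to 0.5 SD per year, a 6-month gap in means gives 5.4 to 15.9% and a 12-month gap gives 6.7 to 47.8%, a range too wide to size the effect.

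**The case against.** The strongest reply is that the bias scenario is not in the plan. A reader might infer that controls will be recruited in one short campaign, but no section says so. Volunteers answering websites and a database with yearly consent renewal fit rolling recruitment just as well. If controls are sought as each patient enrols, they would follow patients through the window and season would largely balance. This stands: the documents support only that clustering can occur.

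A reader might also take 16 to 31% or 28 to 54% as the expected error. Those rates need all 30 controls in one block centred on the seasonal peak or trough, so they are ceilings.

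On storage, a reader might cite a gap of about 27 months. That is the distance between the first and last individuals, not between group means. Storage at -80 degrees Celsius and a single assay session are safeguards, and the single session removes between-session assay variation. P1NP, CTX and sclerostin have no sized effect, and the documents offer no basis for a claim of scanner or operator drift.

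Finally, vitamin D and PTH are supporting outcomes. The hypothesis in II.C names HR-pQCT, BMSi, balance and fall risk, and the sample size rests on trabecular density.

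What remains is that a stated group comparison has no protection against seasonal imbalance in either design or analysis. Relying on later adjustment alone is weaker, because it works poorly if controls cluster in months with few patients.

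**Conclusion.** The point holds as a gap in the plan, not as a demonstrated bias. Examination date is neither matched nor adjusted for, and control dates are not given. If control visits fall in a different part of the year, the vitamin D comparison, and possibly the PTH comparison, would be confounded by season.

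Full clustering gives a false-positive rate of about 10 to 18% (half-year) or 16 to 30% (quarter) averaged over block timing, against a nominal 5%; partial clustering gives less. These figures rest on the assumed amplitude, SD and even spread of patients. Only vitamin D has been sized.

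Storage time is a minor secondary matter, with a difference in group means of at most about 14 months if patients are spread evenly and controls are seen within the same window. The documents do not support extending the point to scanner or operator drift, or to the study's main hypothesis. It is a cheap improvement to supporting outcomes.

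**What to change.** - **III.B:** add that each control is examined in the same calendar season as the matched patient where feasible.
- **V.A:** compare vitamin D and PTH with a regression on group plus month or season of sampling, transforming skewed values if needed, since the listed tests cannot carry a covariate.
- **Reporting:** give sampling date and storage time by group.
- **Assay:** within the planned single session, place each matched pair's samples on the same plate.

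The cost is scheduling: control recruitment must run alongside patient recruitment, and the model gains a term or two. No extra participants or procedures are needed. The 28 per group and 80% power for trabecular density are unchanged.

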### Inclusion criteria for the acromegalic group:

- 1. Verified acromegaly diagnosis
- 2. Age  $\geq 18$  years
- 3. Ability to provide informed consent
- 4. Ability to stand on both legs for  $\geq$ 5 minutes at a time and walk  $\geq$ 6 meters
- 5. Patient is eugonadal, either naturally or by hormone replacement therapy

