#### Exclusion criteria for the acromegalic group:

- 1. Established diagnosis of severe kidney or liver dysfunction, malabsorption, multiple myeloma or other diseases associated with reduced bone quality
- 2. Treatment with supraphysiological doses of glucocorticoids or other drugs that impair bone quality
- 3. Diagnosis of rheumatoid arthritis, psoriatic arthritis or other joint diseases unrelated to acromegaly
- 4. Active drug or alcohol abuse
- 5. Pregnancy
- 6. Known allergy/hypersensitivity to local anaesthetics or disinfectant
- 7. Other factors that render the subject unable to participate in the clinical study, based on the judgment of the investigator(s)

The control subjects will be recruited via social media, the aforementioned database and websites, and matched to the acromegalic study population.

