#### Inclusion criteria for the control group:

- 1. Age  $\geq 18$  years
- 2. Ability to provide informed consent
- 3. Ability to stand on both legs for  $\geq$ 5 minutes at a time and walk  $\geq$ 6 meters

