#### Exclusion criteria for the control group:

- 1. Established diagnosis of severe kidney or liver dysfunction, malabsorption, multiple myeloma, diabetes or other diseases associated with reduced bone quality
- 2. Treatment with supraphysiological doses of glucocorticoids or other drugs that impair bone quality
- 3. Diagnosis of rheumatoid arthritis, psoriatic arthritis or other joint diseases
- 4. Active drug or alcohol abuse
- 5. Pregnancy

Research protocol – Acromegaly: balance, falls and fracture risk

- 6. Known allergy/hypersensitivity to local anaesthetics or disinfectant
- 7. Other factors that render the subject unable to participate in the clinical study, based on the judgment of the investigator(s)

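### Eugonadal status is required of patients but not of controls, natural menopause is left unclassified, and menopausal status is not among the data to be collected

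*Combined protocol and SAP*

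**What the plan says.** Section III.B lists as the fifth inclusion criterion for patients: "Patient is eugonadal, either naturally or by hormone replacement therapy". No hormone threshold is given, and nothing says how a woman past natural menopause and not on hormone therapy is classified.

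Under "Inclusion criteria for the control group" there are three items: age, consent, and ability to stand and walk. None concerns gonadal status. The nearest control exclusion covers "multiple myeloma, diabetes or other diseases associated with reduced bone quality", and the patient list has a parallel item, "multiple myeloma or other diseases associated with reduced bone quality". This could plausibly remove diagnosed hypogonadism, but natural menopause is not a disease. The 30 "sex-matched non-acromegalic control subjects" are also matched on age (within 5 years) and BMI (within 5 points), but not on menopausal status or hormone therapy.

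Section II.B explains why the factor matters: "Secondary hypogonadism due to tumor mass effect or pituitary surgery plays a significant role in the diminished bone quality of acromegalic patients". It also ranks hypogonadism with disease duration among the most influential risk factors.

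On data, section III.D (Questionnaires) collects medicine lists from everyone, and section IV names age, sex and medicine use. Menopausal status is not named. The assays in section III.D are P1NP, CTX, sclerostin, vitamin D and PTH, with no sex hormones. Section V.A names t-tests, chi-squared tests and Mann-Whitney U tests, all unadjusted, as examples of the group comparisons.

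**The concern.** The protocol identifies a strong determinant of bone quality and then controls it by eligibility in one group only. Restricting patients is sensible in itself, because it separates the effect of acromegaly from that of untreated hypogonadism. The comparison with controls is clean only if controls meet the same rule.

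The wording can be read in two ways. Set in a pituitary background, it may mean only that pituitary hypogonadism is absent or replaced. Taken literally, an untreated postmenopausal woman might be judged eugonadal neither naturally nor by replacement, and so be ineligible as a patient while remaining eligible as a control. Two screeners could decide differently.

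Under the literal reading, untreated postmenopausal controls would be expected to lower the control mean for trabecular density and raise control P1NP and CTX. Those contrasts would then move toward no difference. Trabecular density is the parameter on which the study is powered. The data named could not fully show or correct the imbalance: medicine lists reveal hormone therapy, but do not separate premenopausal women from untreated postmenopausal women close to the age of menopause. Stored blood could be assayed later only where separate consent was given and after a renewed ethics application (sections III.D and VIII.A).

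**Working it through.** **Inputs from the documents.** Trabecular density means of 180 (controls) and 150 (patients), SD 40, alpha 5%, 28 per group, power 80% (section V.A); planned enrolment of 30 per group (section III.B). Sidedness is not stated; two-sided reproduces the figure.

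**Inputs that are assumptions.** f, the excess share of controls who are untreated postmenopausal compared with patients; m, their deficit in trabecular density; and a half-female sample in step 4. The documents give none of these.

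**Step 1: the plan's own figure.** The standard error at 28 per group is 40 × √(2/28) = 10.69. Then 30/10.69 − 1.96 = 0.85, and the normal approximation gives 80.1%, so the stated 80% reproduces. The noncentral t gives 78.7%. At 30 per group the standard error is 40 × √(2/30) = 10.33 and the t-based power is 81.5%.

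**Step 2: where an excess could come from.** Under the pituitary reading, untreated postmenopausal women are eligible in both groups, and age and sex matching keeps f near zero. Under the literal reading, a barred patient generates no matched control. An excess then arises mainly from (i) controls matched to hormone-treated women of menopausal age and (ii) controls on the other side of menopause within the 5-year window. Men and clearly premenopausal women add little. I take f = 5-15%, that is 0.05 × 30 = 1.5 to 0.15 × 30 = 4.5 controls, and m = 10-20 units.

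**Step 3: effect on the powered contrast.** Shift = f × m; expected difference = 30 − shift; two-sided t-test, SD 40.

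| f | m | Shift | Shift / 10.33 | Difference | Power, 30 per group | Power, 28 per group |
|---|---|---|---|---|---|---|
| 0 | any | 0 | 0 | 30 | 81.5% | 78.7% |
| 0.05 | 10 | 0.5 | 0.05 | 29.5 | 80.2% | 77.3% |
| 0.05 | 20 | 1.0 | 0.10 | 29.0 | 78.8% | 75.9% |
| 0.15 | 10 | 1.5 | 0.15 | 28.5 | 77.4% | 74.5% |
| 0.15 | 20 | 3.0 | 0.29 | 27.0 | 72.9% | 69.9% |

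**Step 4: price of an adjusted analysis.** Use three levels: men; premenopausal or hormone-treated women; untreated postmenopausal women. Variance inflation = 1/(1 − R²), with R² from regressing group on level: R² = Σ (pooled share) × (patient fraction − 0.5)² / 0.25.

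- f = 15%, half women, no untreated patients: pooled shares 0.5, 0.425, 0.075; patient fractions 0.5, 0.588, 0. R² = (0.425 × 0.0078 + 0.075 × 0.25)/0.25 = 0.088, inflation 1.097, power for 30 units at 30 per group 77.8%.
- f = 5%: pooled shares 0.5, 0.475, 0.025; patient fractions 0.5, 0.526, 0. R² = 0.026, inflation 1.027, power 80.4%.
- Balanced: inflation 1, power 81.5%.

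These figures ignore any gain in precision from the covariate.

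**The case against.** The strongest reply is that the criterion is about the pituitary. The gonadal discussion in section II.B concerns hypogonadism from the tumour or its surgery, and nothing says that a patient past natural menopause is ineligible. That reading is the more natural one, and under it the shift is near zero. This stands: the documents show a missing definition and a one-sided rule, not a demonstrated bias.

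Matching also limits the damage on the literal reading, because controls are recruited to match patients already eligible. A reader might infer an imbalance of 15-30% and power as low as 62.8% (30% × 20 = 6 units at 30 per group). The documents do not support that. With half the sample women, 30% means 9 of 15 control women untreated with no patient counterpart, so about 9 of 15 female patients would have to be on hormone therapy at menopausal age or mismatched across menopause.

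The net direction is not certain either. Patients now on replacement may carry bone loss from earlier hypogonadism, which would widen the contrast. That does not arise from the asymmetric criterion, but it argues against forecasting attenuation overall.

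Some protection already exists. Controls are described as healthy, the disease and investigator-judgment exclusions can remove known hypogonadism, and medicine lists show hormone therapy. Neither the patient record data nor the list of tests is closed. This helps with diagnosed hypogonadism but does not classify natural menopause.

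A reader might also suspect bone-protective drugs, which are not excluded by name. Nothing in the documents indicates that use would differ between groups, so no point is made of it.

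**Conclusion.** The asymmetry is real: gonadal status is an eligibility condition for patients only, natural menopause is unclassified, and menopausal status is not among the data named. The consequence is conditional. Under the pituitary reading it is negligible. Under the literal reading the trabecular density, P1NP and CTX contrasts would move somewhat toward no difference. For density the assumed range is 0.5-3 units, or 0.05-0.29 standard errors, taking power at 30 per group from 81.5% to between 80.2% and 72.9%. Those figures rest on assumed values of f and m, and on extending the protocol's evidence about hypogonadism in acromegaly to natural menopause in controls.

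The concern is weaker for BMSi, since the one acromegaly study cited found lower values "regardless of biochemical control, hypogonadism or presence of vertebral fractures". Nor is the restriction of patients at fault: section II.B notes a deficit that persists in eugonadal patients ("although even eugonadal acromegalic patients have reduced trabecular bone quality"). It would go too far to conclude that the bone comparisons are shown to be biased or that the sample size is miscalculated; the stated 80% reproduces. This is a minor-to-moderate improvement.

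**What to change.** 1. State one definition of eugonadal, including how natural menopause is classified, and apply it to both groups. Which definition to adopt is for the investigators. A common rule also covers hypogonadism in male controls, which a menopausal covariate cannot.
2. Record menopausal and hormone-therapy status in all women at the study visit.
3. Pre-specify one supportive analysis of the bone outcomes (vBMD, BMSi, P1NP, CTX) adjusted for the three-level status used in step 4 of the working.

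The cost is eligibility wording, one or two screening questions for women, slightly more screening of controls, and one extra analysis. The adjusted analysis loses little power: 81.5% if status is balanced, which the common rule promotes, and 80.4% or 77.8% if 5% or 15% of controls are untreated with no patient counterpart, on the step 4 assumptions. It should be read as supportive. If only pituitary hypogonadism was meant, one sentence saying so largely settles the matter. Recording the status at the visit is still worthwhile, because it may be hard to recover afterwards.
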